7.3. Other Efficacy Analyses

7.3.1. Total Endoscopic Nasal Polyps Score Responders

A responder is defined as a participant achieving a ≥ 1 -point improvement (decrease) from baseline in total endoscopic NP score (based on centrally read data) at Week 52. Participants with missing data at Baseline or Week 52 (due to early study withdrawal or any other reason) will be included in the analysis as a non-responder.

7.3.1.1. Summary Measure

The summary measure of treatment effect will be the odds ratio which represents the relative odds of a participant being a responder in the mepolizumab arm compared with placebo.

7.3.1.2. Population of Interest

The population of interest is the ITT population.

7.3.1.3. Strategy for Intercurrent (Post-Randomization) Events

See Section 7.1.4. for details.

7.3.1.4. Statistical Analyses / Methods

Endpoint / Variables					

 Total endoscopic nasal polyps score responders Participants with a ≥ 1-point improvement from baseline in total endoscopic NP at Week 52 (based on centrally read data) will be included in the analysis as a responder. The following participants will be included in the analysis as a non-responder: 
 Participants who had actual surgery prior to Week 52 Participants who withdrew early from the study or who had missing data at Baseline or Week 52 					
Model Specification					

 A logistic regression model will be used to compare the proportion of responders in the mepolizumab arm compared to placebo. The odds ratio comparing treatment groups will be estimated using the observed marginal distribution of the sample covariates. The analysis model will include the following terms: 
 
 Fixed Categorical:	Treatment group, Region	
 
 Fixed Continuous:	Baseline score, Log_e baseline blood eosinophil count	
 
 
 Participants with missing covariate information will be excluded from the analysis 		Fixed Categorical:	Treatment group, Region	Fixed Continuous:	Baseline score, Log_e baseline blood eosinophil count
Fixed Categorical:	Treatment group, Region				
Fixed Continuous:	Baseline score, Log_e baseline blood eosinophil count				
Model Checking & Diagnostics					

 Models will be checked for issues with convergence. 					
Model Results Presentation					

 The number and percentage of participants identified as responders and non-responders for analysis will be displayed by treatment group, the non-responder group will be further categorized to display the number of participants with actual surgery, the number withdrawn early from the study and the number with missing baseline data. The estimated odds ratio, 95% CI and p-value comparing treatments from the logistic regression model will be displayed. A forest plot of the estimated odds ratio and 95% CI for the comparison of treatment groups will be provided by visit. 					

Subgroup Analyses

- No subgroup analyses are planned for this endpoint.

Sensitivity and Supportive Analyses

- No sensitivity/supportive analyses are planned for this endpoint.

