For the purpose of inclusion into this study, NP surgery is defined as any procedure involving instruments with resulting incision (cutting open) and removal of the polyp tissue from the nasal cavity (polypectomy). Any procedure involving instrumentation in the nasal cavity resulting in dilatation of the nasal passage such as balloon sinuplasty, insertion of coated stents or direct injection of steroids or other medication without any removal of NP tissue does not fulfil this criterion. This is because there is no significant reduction in overall eosinophilic load in the nasal cavity. Consequently, it is difficult to discern whether any recurrence of NP disease after such procedures is actually driven by eosinophilia or not.

Any nasal surgical procedures can influence the co-primary endpoints, as can dilatation of the air passages (eg balloon sinuplasty) in the nasal cavity, therefore the impact of occurrence of either surgery or sinuplasty will be taken into consideration when assessing efficacy endpoints. As stated above, actual surgery is an important secondary efficacy endpoint. Evaluation of this key secondary endpoint will be based only on invasive procedures involving instruments resulting in incision and removal of tissue (eg polypectomy). Diagnostic or investigative procedures such as nasal endoscopy would not be considered as surgery.

To ensure that this study can detect a difference in surgical outcome between the two treatment arms, participants, whom in the opinion of the investigator are contraindicated for NP surgery, will be excluded.

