7.1.4. Strategy for Intercurrent (Post-Randomization) Events

The anticipated intercurrent events occurring prior to Week 52 for the co-primary endpoints are: Surgery/sinuplasty, which includes any procedure involving instruments resulting in incision and removal of tissue (e.g. polypectomy) or dilatation of the air passages (e.g. balloon sinuplasty) in the nasal cavity and premature discontinuation of interventional product.

For each co-primary endpoint, the anticipated intercurrent event of surgery/sinuplasty will be handled using a composite strategy such that the occurrence of the event is incorporated into the definition of the endpoint. In participants who do not experience surgery/sinuplasty, the anticipated intercurrent event of premature discontinuation of interventional product will be handled using a treatment policy strategy, such that in these participants all data reported at week 52 for total endoscopic NP score (or during the 4-week period prior to Week 52 for nasal obstruction VAS) will be included in the analysis, regardless of discontinuation from treatment.

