7.3.5.4. Statistical Analyses / Methods**Endpoint / Variables**

- Need for surgery at week 52 will be assessed for each participant as detailed in Section 14.6.5.
- The following participants will be included in the analysis as still having a need for surgery:
 - Participants who had surgery prior to Week 52
 - Participants who withdrew early from the study or who had missing data at Baseline or Week 52

Model Specification					

 A logistic regression model will be used to compare the proportion of participants who no longer have a need for surgery in the mepolizumab arm compared to placebo. The odds ratio comparing treatment groups will be estimated using the observed marginal distribution of the sample covariates. The analysis model will include the following terms: 
 
 Fixed Categorical:	Treatment group, Region	
 
 Fixed Continuous:	Baseline total nasal polyps endoscopic score (centrally read data), Baseline overall VAS score, Log_e baseline blood eosinophil count	
 
 
 Participants with missing covariate information will be excluded from the analysis 		Fixed Categorical:	Treatment group, Region	Fixed Continuous:	Baseline total nasal polyps endoscopic score (centrally read data), Baseline overall VAS score, Log _e baseline blood eosinophil count
Fixed Categorical:	Treatment group, Region				
Fixed Continuous:	Baseline total nasal polyps endoscopic score (centrally read data), Baseline overall VAS score, Log _e baseline blood eosinophil count				
Model Checking & Diagnostics					

 Models will be checking for issues with convergence. 					
Model Results Presentation					

 The number and percentage of participants identified as no longer having a need/still having a need for surgery will be displayed by treatment group, the still having a need for surgery group will be further categorized to display the number participants with actual surgery, the number withdrawn early from the study and the number with missing Baseline data. The estimated odds ratio, 95% CI and p-value comparing treatments from the logistic regression model will be displayed. 					
Subgroup Analyses					

 No subgroup analyses are planned for this endpoint. 					
Sensitivity and Supportive Analyses					

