14.6.5. Efficacy

Assigning the worst score for subjects with surgery or missing data
Relevant efficacy endpoints

 Subjects who undergo surgery/sinuplasty will have their worst observed score (or worst observed 4-week mean) assigned for all subsequent visits (or 4-week periods) following surgery/sinuplasty. The assigned value will be the worst observed value from baseline up to before the surgery/sinuplasty. Assessments taking place on the same day as surgery/sinuplasty are assumed to have been carried out before the surgery/sinuplasty. Subjects who have not experienced surgery/sinuplasty and have missing values due to study withdrawal, will have their worst observed score (or worst observed 4-week mean) assigned for all missing visits (or 4-week periods) following study withdrawal. The assigned value will be the worst observed value from baseline up until study withdrawal. Subjects with missing data for other reasons will have their worst observed score (or worst observed 4-week mean) prior to the missing visit (or missing 4-week period) assigned.
Total Endoscopic Nasal Score
Responder

 A responder will be defined as a participant with a ≥1-point improvement from baseline in total endoscopic nasal score (centrally read). Participants with no improvement/worsening or with missing data will be considered a non-responder for analysis.
VAS scores (individual and composite)
Individual VAS Scores

 VAS scores are captured electronically using an eDiary. participants indicate their response on a line CCI - This section contained Clinical Outcome Assessment data collection questionnaires or indices, which are protected by third party copyright laws and therefore have been excluded. The final VAS scores for inclusion in summary and analysis tables will be derived from the electronically captured score by CCI.
Change from baseline categories

 The baseline scores will be calculated as the mean of the scores reported between the 7 days prior to the first dose. The scores for each 4-week period will be calculated as the mean of the scores reported between timepoints detailed in Section 14.3.3.
Composite VAS scores

VAS scores (individual and composite)

- Two separate composite VAS scores will be derived using the final VAS scores:
- Composite of nasal obstruction, nasal discharge, mucus in the throat and loss of smell

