 - CCI [REDACTED]
- Composite of nasal obstruction, nasal discharge, mucus in the throat, loss of smell and facial pain
 - CCI [REDACTED]

Nasal Surgery (reported on the disease related events page of the eCRF)
Time to first nasal surgery

 Calculated as (Date of first nasal surgery – Date of first dose of study treatment) + 1 Analysis excluding data from the follow-up period after Week 52: For participants who withdraw from the study before Week 52 and before experiencing surgery, event times will be censored at the time of study withdrawal For participants who complete to Week 52 without experiencing surgery, event times will be censored at the time of the Week 52 visit. Analysis including data from the follow-up period after Week 52: For participants who withdraw from the follow-up period before completion and before experiencing surgery, event times will be censored at the time of study withdrawal. For participants who complete the follow-up period without experiencing surgery, event times will be censored at time of completion of follow-up.
Need for surgery

 Need for surgery at Week 52 is based on the overall VAS symptoms score and the endoscopic NP score (centrally read). Participants will be classified as having a need for surgery if they meet the following: 
 Overall VAS symptoms score >7 (Weeks 49-52) and total endoscopic NP score ≥5 (Week 52, centrally read) Participants who have undergone nasal polyps surgery at any time prior to the week 52 visit, or who have a missing endoscopic NP score (centrally read) at Week 52, or missing overall VAS symptom score (Weeks 49-52) will be identified for analysis as still having a need for surgery.
Rate of surgery

 The crude rate of surgery will be presented for each treatment arm, this will be calculated as: $\left(\frac{\text{Total number of nasal surgeries}}{\text{Total number of days in the study}} \right) * 365.25$

Systemic steroid use
Conversion of glucocorticoid dose to mgs of prednisolone equivalent OCS use

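### The SAP gives two conflicting rules for balloon sinuplasty in the NP responder, SNOT-22 responder and need-for-surgery endpoints

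*SAP*

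**What the plan says.** Three *other* endpoints are involved: NP score responders (SAP 7.3.1), SNOT-22 responders (7.3.3) and need for surgery (7.3.5).

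**Strategy sections.** 7.3.1.3 reads "See Section 7.1.4. for details", and 7.3.3.3 and 7.3.5.3 say the same. Section 7.1.4 names the event as "Surgery/sinuplasty, which includes any procedure involving instruments resulting in incision and removal of tissue (e.g. polypectomy) or dilatation of the air passages", and states that "the anticipated intercurrent event of surgery/sinuplasty will be handled using a composite strategy".

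**General derivation rule.** The first block of 14.6.5, labelled as covering relevant efficacy endpoints, says: "Subjects who undergo surgery/sinuplasty will have their worst observed score (or worst observed 4-week mean) assigned for all subsequent visits". The window for the worst score runs from baseline to just before the procedure. The endpoints covered are not listed.

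**Explicit failure lists.**
- 7.3.1.4 and 7.3.3.4: "Participants who had actual surgery prior to Week 52"
- 7.3.5.4: "Participants who had surgery prior to Week 52"
- 14.6.5, need-for-surgery rule: "Participants who have undergone nasal polyps surgery at any time prior to the week 52 visit"

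Each also makes withdrawal or missing data a failure. None mentions sinuplasty. The breakdown of failures planned for display (7.3.1.4, used by 7.3.3.4, and 7.3.5.4) has no category for it.

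**The concern.** Protocol 5.1 recognises that dilatation of the air passages can affect the co-primary measures, and commits to taking surgery or sinuplasty into account when efficacy endpoints are assessed. The failure lists do not carry that through. Read literally, a participant who has balloon sinuplasty in Week 20 and a lower score at Week 52 fails in the co-primary analysis and succeeds in the responder analysis. The effect of a procedure would then be credited to the assigned treatment.

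The gap appears to come from Amendment 4. Its summary of changes shows that the NP surgery definition formerly included dilatation, so *actual surgery* in the superseded analysis plan could cover sinuplasty. The definition was narrowed, but the responder lists kept their wording. Other sections were updated to surgery/sinuplasty: waiting list (7.3.7), PnIF (7.3.10), SF-36 (7.3.11.1) and ACQ-5 (7.4). The need-for-surgery list was edited from *actual surgery* to *surgery*, still without sinuplasty.

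**Working it through.** **1. What surgery now covers.** Protocol 9.2.3 defines NP surgery as an endpoint by incision and removal of tissue. SAP 7.2.1 excludes dilatation from the time-to-surgery endpoint. With no other definition given, *actual surgery* does not include sinuplasty on its face.

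**2. One participant under each rule** (sinuplasty in Week 20, improved at Week 52).

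| Endpoint | Lists applied to observed Week 52 data | 7.1.4 with the 14.6.5 worst-score rule |
|---|---|---|
| Co-primary NP score | not applicable | worst pre-procedure score assigned |
| NP responder (decrease of at least 1) | responder if the threshold is met | non-responder |
| SNOT-22 responder (decrease of at least 8.9) | responder if the threshold is met | non-responder |
| Need for surgery (overall VAS >7 and NP ≥5) | no longer in need if either criterion fails | still in need, with one exception |

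**3. Why the right-hand column follows.** Let b be the baseline score. The assigned score is the maximum of b and all later pre-procedure scores. The assigned change is that maximum minus b, so it is at least 0. It cannot reach −1 (NP) or −8.9 (SNOT-22).

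For need for surgery, randomisation criterion 2 requires a mean overall VAS above 7 in the week before Visit 2, so the assigned VAS stays above 7. The NP score is less certain. Eligibility uses the Visit 1 central reading (3 + 2 = 5 at least), while baseline is the Day 1 reading (SAP 5.2.1). If the Day 1 score and all later pre-procedure scores are below 5, the assigned NP score is below 5 and the participant is no longer in need. That is the exception.

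**4. Which rule governs?** The text does not settle it.
- The worst-score rule also fills Week 52 values missing through withdrawal or other reasons. Yet 7.3.1, 7.3.3, 7.3.5 and their methods sections give a separate missing-data rule. It has little to do unless observed data are used.
- In the efficacy table list (14.12.6), Tables 2.39 and 2.44 carry a note to use the dataset with assigned values. Tables 2.40, 2.43 and 2.45, for the three endpoints here, do not. This is only supportive: Table 2.2, the co-primary NP analysis, also lacks the note.

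**5. Planning figure.** Protocol 10.1 gives one-point NP improvement in 27% (placebo) and 52% (mepolizumab), with 200 per arm and power over 90%. With the two-proportion formula (pooled variance under the null, two-sided 5%):
- null SE = √(2 × 0.395 × 0.605 / 200) = 0.0489
- alternative SE = √((0.27 × 0.73 + 0.52 × 0.48) / 200) = 0.0473
- z = (0.25 − 1.96 × 0.0489) / 0.0473 ≈ 3.26, so power is 99.9%

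The stated figure is consistent. The point does not depend on it.

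**6. Illustration of the literal reading.** The documents give no sinuplasty rate. Assume 2% or 5% of an arm (4 or 10 of 200) are moved from non-response to response. Unadjusted odds ratio = [p_M / (1 − p_M)] / [p_P / (1 − p_P)].

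| Moved to response | p_P | p_M | Odds ratio |
|---|---|---|---|
| none | 0.27 | 0.52 | 2.93 |
| 2% placebo only | 0.29 | 0.52 | 2.65 |
| 5% placebo only | 0.32 | 0.52 | 2.30 |
| 2% both arms | 0.29 | 0.54 | 2.87 |
| 5% both arms | 0.32 | 0.57 | 2.82 |
| 2% mepolizumab only | 0.27 | 0.54 | 3.17 |
| 5% mepolizumab only | 0.27 | 0.57 | 3.58 |

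**The case against.** The strongest answer is that the SAP already handles sinuplasty. All three endpoints adopt 7.1.4 explicitly. The worst-score rule in 14.6.5 names surgery/sinuplasty and makes an NP or SNOT-22 response impossible. The lists are not said to be exhaustive, so they can be read as adding to those rules. The redundant missing-data rule is not a contradiction either, since both routes give a failure for NP and SNOT-22.

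The SAP also uses *surgery* as shorthand elsewhere. The heading of the worst-score block mentions only surgery above a surgery/sinuplasty rule, and the obstruction VAS paragraph in 7.1.1 does something similar. For event reporting, Protocol 9.3.6 counts sinuplasty within nasal polyp surgery, and 14.6.5 takes nasal surgery from that case report form page.

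Much of this stands. A reader might infer that the plan counts improvement after sinuplasty as a treatment response. The documents do not support that as a flat statement, because 7.1.4 and the worst-score rule point the other way. A reader might also take the SNOT-22 domain scores (7.3.4) as a further instance, since that text names only actual surgery. It is not one: it defers to 7.1.4 for the handling.

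The objection does not remove the ambiguity. The relevant endpoints are not enumerated, the term in the lists was narrowed by amendment, and neighbouring sections were updated while these were not. Two programmers could each follow the SAP and classify the same participant differently.

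**Conclusion.** The SAP is internally inconsistent on sinuplasty for these three endpoints. Applied as written to observed Week 52 data, the lists make a participant who improves after sinuplasty a success. Under 7.1.4 and the worst-score rule the participant is a non-responder for NP and SNOT-22, and still in need of surgery except in the Day 1 case above. The latter conclusion rests on the worst-score window including baseline, as 14.6.5 indicates, and on the participant having met the VAS randomisation criterion.

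The consequence is limited. These endpoints are outside the hierarchy in SAP 5.5, so the co-primaries, type I error and sample size are untouched. The odds ratios above apply only if the lists override the other rules, and they use assumed sinuplasty rates. A reader might infer a bias in one direction, but the documents do not support that: misclassification on placebo alone would understate the mepolizumab effect, and on mepolizumab alone would overstate it. The point is worth settling before unblinding because the correction is cheap and the two readings disagree on individual participants.

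**What to change.** - In 7.3.1.4, 7.3.3.4, 7.3.5.4 and the need-for-surgery rule in 14.6.5, replace *actual surgery*, *surgery* and *nasal polyps surgery* with surgery/sinuplasty as defined in 7.1.4. For need for surgery this also closes the Day 1 exception, because the procedure itself becomes the failure.
- Add sinuplasty to the non-responder and still-in-need categories displayed in the tables.
- Align the wording of 7.3.4. Its handling does not change.
- Leave the definition of the key secondary endpoint, time to first nasal surgery, as it is.

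The cost is SAP wording and one extra display category. Protocol 9.2.3 already requires sinuplasty to be recorded at each visit, and the co-primary dataset already needs that information, so no new data are required.

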7.3.2. Change from Baseline in Mean Individual and Composite VAS Symptom Scores

Participants rate individual symptoms daily on a visual analogue scale using an eDiary, the scale range for each symptom is ^{CCI} [REDACTED]

[REDACTED] Change from baseline during the 4-weeks prior to Week 52 in mean individual VAS symptom scores for nasal discharge, mucus in throat and facial pain and the mean composite VAS score (combining nasal obstruction, nasal discharge, mucus in the throat, loss of smell and facial pain), will be analysed as detailed for the co-primary endpoint of change from baseline in mean nasal obstruction VAS score during the 4 weeks prior to Week 52.

Details regarding the summary measure, population of interest and the strategy for intercurrent events are provided in Section 7.1.2 to Section 7.1.4.

7.3.2.1. Statistical Analyses / Methods**Endpoint / Variables**

- Change from baseline in individual VAS symptom scores of nasal discharge, mucus in throat and facial pain during the 4 weeks prior to Week 52
- Change from baseline in mean composite VAS score (combining nasal obstruction, nasal discharge, mucus in the throat, loss of smell and facial pain) during the 4 weeks prior to Week 52

Model Specification

- For each endpoint the p-value for the difference in median change from baseline between treatments will be based on the non-parametric Wilcoxon rank-sum test.
- The difference in median change from baseline with 95% confidence intervals will be estimated by quantile regression using a bootstrap approach.
- The analysis model will include the following terms:

Fixed Categorical:	Treatment group, Region
Fixed Continuous:	Baseline score, Log _e baseline blood eosinophil count

- Participants with missing covariate information will be excluded from the analysis

Model Checking & Diagnostics

- Models will be checked for issues with convergence.

Model Results Presentation

- Median change from baseline within each treatment group.
- Estimated difference between treatments in median change from baseline with 95% confidence

interval (CI). 
 • p-value comparing treatment groups from the Wilcoxon rank-sum test. •
Subgroup Analyses

 • No subgroup analyses are planned for these endpoints.
Sensitivity and Supportive Analyses

 • No sensitivity/supportive analyses are planned for these endpoints.

